Central line associated blood stream infections (CLABSIs) are one of the most deadly types of hospital-acquired infections (HAIs), with a mortality rate of 12% to 25%.¹ Nationally, hospital acquired CLABSIs are reported as a measure of patient safety through the National Healthcare Safety Network. The Center for Disease Control and Prevention (CDC) collects data and reports on CLABSIs among hospitalized patients aged 1 year or older and among patients receiving outpatient hemodialysis.² It is estimated that 84,551 to 204,901 CLABSIs occur each year resulting in 10,426 to 25,145 preventable deaths.³ The cost of each CLASBI is estimated to range from \$3,700 to \$45, 254.⁴ If the average mortality caused by CLABSIs is 18% (reported ranges 15-24%) and the average CLASBI rate is 5.3 per 1000 catheter-days, as many as 28 000 patients die of CLABSIs annually in ICUs alone.³⁻⁵ Because of the high incidence, mortality rate and healthcare costs of CLABSIs, the Agency for Healthcare Research and Quality (AHRQ) sponsored a national patient safety imperative aimed at eliminating CLABSIs.⁴ This program reviewed data from over 1000 hospitals in 44 states in the US including ICU, non-ICU and pediatric unit settings. It implemented a Comprehensive Unit-based Safety Program (CUSP) directed towards reducing central line associated blood stream infections. The program bundled interventions of establishing safety cultures on a unit level with utilization of safety teams and implementation of CLASBI reduction steps. These CLASBI reduction steps included: appropriate hand hygiene, full barrier precautions with line insertion, daily review of line necessity, chlorhexidine skin care, and avoidance of femoral site placement of central lines. With use of these methods, CLASBI rates were reduced 40%.⁶ While much of healthcare is being diverted to the outpatient setting, no such efforts have been undertaken in evaluating outpatient CLABSIs with the exception of the dialysis population.

Individuals undergoing hematopoietic stem cell transplantation (HSCT) usually require central venous access for frequent infusions including chemotherapy and blood products as well as for hydration, electrolyte replacement, antibiotics, and parenteral nutrition. However, the benefits of having a central line must be balanced against the risk of complications, the most common of which is central line-associated bloodstream infections (CLABSIs).⁷⁻⁹ Risk factors established for the development of CLASBI include prolonged hospitalization before catheter placement, prolonged duration of catheterization, microbial colonization of the insertion site or catheter hub, internal jugular or femoral catheterization, neutropenia, TPN, transfusion of blood products and frequent manipulations of the catheter. (¹⁰⁻¹⁶) Care of patients undergoing a HSCT is

complex and these individuals collect many of the known factors, which put them at risk for developing CLASBIs. As well, chemotherapy often induces mucositis resulting in translocation of enteric microorganisms into the bloodstream, which may then secondarily seed central venous access devices.^{17,18} In an effort to reduce bacteremia in HSCT patients expected to have a prolonged period of neutropenia, antimicrobial prophylaxis with agents having activity against enteric pathogens is common practice.

With engraftment, the absolute neutrophil count rises, prophylactic antimicrobials are discontinued, and mucositis resolves. HSCT patients may be released to home requiring infusion of fluids, electrolytes, TPN, and sometimes antimicrobial agents. As well, these patients have frequent outpatient visits for transfusion of blood products. Due to chemotherapy induced phlebitis of peripheral veins, the central line is frequently the only intravenous access available to obtain blood for laboratory monitoring of the patient. Therefore, patients who have undergone HSCT have multiple persistent risk factors for the development of CLABSI, even after discharge from the inpatient setting.

Chlorhexidine is a broad-spectrum antiseptic agent active against both gram-positive and gram-negative bacteria as well as yeasts, and has been successfully assessed as an effective skin antiseptic alone or in combination with alcohol.¹⁹⁻²⁹ Due to its success in reducing hospital acquired CLASBIs, daily chlorhexidine baths have been implemented in the intensive care setting and in inpatient stem cell transplant units. In this study we aim to evaluate whether or not continued skin decontamination with 2% chlorhexidine impregnated washcloths, used after routine bathing, will reduce the incidence of CLASBIs in the HSCT population after discharge for as long as the central line is in place or 14 weeks post discharge, whichever comes first.

Overall Study Design:

This will be single site [University of Chicago (U of C)] prospective, double blinded randomized, controlled clinical trial of daily bathing with no-rinse, 2% CHG-impregnated washcloths (Sage 2% chlorhexidine gluconate cloths; Sage Products Inc., Cary, Illinois) vs placebo chlorhexidine washcloths. The main study outcomes will be primary BSI and clinical (culture-negative) sepsis. Catheter insertion policy for the U of C HSCT program mandates interventional radiology insertion of central venous catheters on the day of admission for HSCT conditioning using sterile technique, full barrier drapes, and insertion site disinfection with 2% CHG. Antiseptic- or antibiotic-coated catheters are not used. While hospitalized, patients follow routine daily 2% CHG baths. Routine catheter care with CHG-Alcohol (Chloraprep) dressing changes and a CHG-biopatch at the insertion site will be done weekly, per standard of care, while inpatient and will continue in the outpatient setting. Prior to discharge, enrolled subjects will be randomized to 2% CHG vs placebo washcloths (supplied as a blinded product) which the patient will continue until end of study. No other catheter-associated BSI infection control interventions will be implemented during the study.

Setting and Participants:

Approximately 200 HSCTs are done annually at the U of C. On admission for transplant, HSCT patients commence use of daily 2% chlorhexidine applied by impregnated washcloths after routine daily washing. This is done as part of standard care in an effort to prevent inpatient CLASBIs. Once patients have demonstrated engraftment of neutrophils (absolute neutrophil count >500 cells/mm³ for 48 hours) routine home bathing instructions are given by the nursing staff in preparation for discharge. These instructions include educating the patient specifically not to allow the central line insertion site to become wet (i.e.: no showers or baths), technique for scrubbing the catheter hub(s), and sterile technique for accessing the line in those who will be performing home IV administration.

The incidence of inpatient hospital acquired (HA) and outpatient present on admission (POA) CLASBIs as evaluated here at the U of C (see table below) has been previously determined and the outpatient data will be used as our initial data control group:

**Number of CLABSI by
Nursing Unit
September 2007 to August
2008**

| Unit | Number of HA-CLABSI | Number of POA-CLABSI |
|--------------|---------------------|----------------------|
| T6NW | 32 | 18 |
| T6NE | 1 | 30 |
| T6SW | 3 | 28 |
| TOTAL | 36 | 76 |

Methods:

Approval of the study protocol will be obtained from the University of Chicago Institutional Review Board.

Subjects:

Approximately 200 HSCT subjects will be enrolled

Inclusion Criteria:

Each patient admitted to the U of C HSCT unit aged ≥ 18 years during the study periods will be approached regarding the study.

Exclusion Criteria:

Patients who have already experienced an allergy or rash related to use of chlorhexidine washcloths or other CHG products will be excluded.

Patients with extensive open wounds will be excluded from the study.

Study Procedures:

Prior to discharge, eligible subjects will be approached for study participation. Those who agree to participate and complete the consent process will be randomized to the active or placebo study arms.

Study Washcloth (2% CHG and placebo) :

Subjects will receive an instruction sheet that illustrates where to use the washcloths.

Use of the washcloths will be done in the following sequential order to rinse all body surfaces, with the exception of the mucous membranes of the eyes and mouth.

First: neck, shoulders and chest; Second: axillae, arms and hands; Third: abdomen then groin and then perineum; Fourth: right leg and foot; Fifth left leg and foot and the Sixth:back of the neck back and buttocks.

Subjects received education on using chlorhexidine washcloths throughout the hospitalization for their HSCT and prior to discharge from the inpatient hospitalization, therefore oversight of the trial will not include direct observation of bathing. There will be no washout period in the transition from the inpatient setting.

The dates of catheter placement will be recorded and used to calculate length of catheter days in place. The discharge date and discharge setting will be recorded. Data will be recorded in RedCap.

Data on all positive blood cultures will be collected for bacterial/fungal pathogens. Incident bacteremia (or fungemia) will include only the first episode of bacteremia / fungemia and will not include duplicate organisms or subsequent infections as the primary aim of the study is to prevent the incident CLABSI. A bacteremia / fungemia will constitute treatment failure. Subjects will stop study product and be followed for 4 weeks for safety assessment (incident of adverse event associated with study product). Hospital admissions will be recorded. Association with study product will be determined. Cost of hospitalizations related to CLASBI will be determined.

A study diary will be used by subjects to confirm compliance with daily bathing. The study staff will ensure the subject is using the proper bathing technique at each weekly visit. This document will be reviewed and collected weekly when the subject comes for routine outpatient central line catheter care. The study diary will also capture compliance with the outpatient central line accessing protocol. As the subject will access their line using the standard practice (sterile technique with chlorhexidine-alcohol preps) the study will collect the data on this process. Additionally subjects will be asked to save all packaging from washcloths used each week and bring this packaging to the weekly outpatient visit. This will allow study staff to note compliance with washing and to ensure subjects have an adequate supply of washcloth packages. The study staff will enter the total quantity of washcloth packages used during the week on a compliance monitoring worksheet.

Length of Study Participation:

Participation will begin at the time of consent prior to discharge. Subjects will use the study washcloths while the central line remains in place or until 14 weeks post HSCT discharge, whichever comes first.

Stopping Rules:

Subjects that are diagnosed with a bacteremia or fungemia will stop use of product after a positive result.

Payment:

Subjects will not receive any payment for participation in the study

Statistical Plan and Considerations:

The plan is to accrue up to 200 subjects, however, after the first 100 subjects complete the study, the data set will be locked and unblinded and the incidence of CLABSI in each group will be determined. If the difference between the groups is highly statistically significant, ($P < 0.001$), the study will be halted. A 'Student's' t Test will be used to determine difference in outcome (bacteremia or no bacteremia) between the two groups.

Assuming that the outpatient setting would have a higher incidence of CLABSI given the previous Infection Control snapshot, recalculating with an ~50% higher outpatient rate, the estimated number of patients would be calculated as:

. sampsi 0.12 0.0485, power(0.8)

Estimated sample size for two-sample comparison of proportions

Test $H_0: p_1 = p_2$, where p_1 is the proportion in population 1

and p_2 is the proportion in population 2

Assumptions:

$\alpha = 0.0500$ (two-sided)

power = 0.8000

$p_1 = 0.1200$

$p_2 = 0.0485$

$n_2/n_1 = 1.00$

Estimated required sample sizes:

$n_1 = 263$

$n_2 = 263$

For our evaluation we based the numbers of patients on the number of HSC transplants performed annually with a reasonable period of time to enroll subjects. Interim analyses will be performed early on to see if a significant difference exists in making it appropriate or not appropriate to continue

Risks and Benefits:

This clinical research involves minimal risk to the patients involved since it involves only the use of two FDA approved bathing products. Potential recognized risks of bathing with chlorhexidine include local skin irritation, allergic reaction and irritation of mucous membranes. The FDA has waved requirement for an IND.

Data Handling and Record Keeping

All data collection files will be password protected and stored on computers belonging to study investigators. Data collected will be entered into the password protected Access database. Personal health information will be maintained with the database during study period, microbiology data, and medical record review. All patients will be assigned a unique study identification number. This number will be accessible only to study investigators and study staff. Any hard copies of datasets will be stored in a locked filing cabinet in the Infectious Diseases Clinical Trials office. After all data are collected, analyzed, and published, linkage between patients and their unique identifier will be destroyed, with the exception of data collected through Infection Control Departments as part of hospital operations. Identified datasets related to infection control activities will be maintained at the primary institution according to hospital operations policy.

References:

1. Centers for Disease Control and Prevention. Guidelines for the prevention of intravascular catheter-related infections. *MMWR Morb Mortal Wkly Rep.* 2002; 51 (No. RR-10): 1-29.
2. Liang SY and Marschall J. Update on Emerging Infections: News from the Centers for Disease Control and Prevention. *Ann Emerg Med.* 2011; 58: 447-450.
4. Agency for Healthcare Research and Quality. *Tools for Reducing Central Line-Associated Blood Stream Infections.* Rockville, MD: Agency for Healthcare Research and Quality; 2014. <http://www.ahrq.gov/professionals/education/curriculum-tools/clabsitools/index.html>.
5. Agency for Healthcare Research and Quality. Appendix 2. Central line-associated bloodstream infections fact sheet. <http://www.ahrq.gov/professionals/education/curriculum-tools/clabsitools/clabsitoolsap2.html>. Published 2015.
6. (Eliminating CLABSI, A National Patient Safety Imperative: Final Report. <http://www.ahrq.gov/professionals/quality-patient-safety/cusp/clabsi-final/index.html>)

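### The plan's only power calculation needs 263 subjects per arm (526), but enrolment stops at about 200, where power for the assumed effect is about 35–46% and is not disclosed.

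*Combined protocol and SAP*

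**What the plan says.** In the combined protocol and SAP, Statistical Plan and Considerations, the enrolment target and interim look come first: "The plan is to accrue up to 200 subjects, however, after the first 100 subjects complete the study", at which point the data are unblinded and compared. The Subjects section agrees on the number: "Approximately 200 HSCT subjects will be enrolled".

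The same statistical section prints one sample-size calculation, a comparison of two proportions with p1 = 0.12, p2 = 0.0485, two-sided alpha 0.05, power 0.80 and equal arms. Under "Estimated required sample sizes" it gives 263 and 263.

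The sentence after the output gives the basis for the actual number: "For our evaluation we based the numbers of patients on the number of HSC transplants performed annually", together with a feasible enrolment period. No power, detectable difference, expected precision or dropout allowance is given for 200 subjects.

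**The concern.** The calculation and the enrolment plan sit in one section but describe trials of different size. The single power figure a reader finds, 80%, belongs to 526 subjects. The trial will have at most 200.

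The consequence lies in how a null result is read. The only comparison specified is a significance test; no effect estimate or confidence interval is planned. If the trial has less than an even chance of detecting the effect it was designed around, P > 0.05 says little about whether chlorhexidine washcloths work. A reader who carries the 80% forward would take it as evidence that they do not.

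**Working it through.** **Inputs** (all from Statistical Plan and Considerations unless noted): p1 = 0.12; p2 = 0.0485; difference d = 0.0715; relative reduction 0.0715/0.12 = 60%; two-sided alpha 0.05 (z = 1.960); power 0.80 (z = 0.842); allocation 1:1; maximum accrual 200 (also in Subjects). I take 12% as the placebo rate. One hundred per arm assumes that the 1:1 ratio in the calculation is the randomisation ratio, and that nobody is lost.

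**1. Reproduce the plan's 263.** With mean proportion p̄ = 0.08425:

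- Uncorrected: n = [1.960·√(2p̄(1−p̄)) + 0.842·√(p1(1−p1) + p2(1−p2))]² / d² = [1.960 × 0.3928 + 0.842 × 0.3895]² / 0.005112 = 235.7.
- Continuity corrected: n′ = (n/4)·[1 + √(1 + 4/(n·d))]² = (235.7/4) × [1 + √(1 + 4/16.85)]² = 262.9, so 263.

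The printed figure is the continuity-corrected one and is right. Even without the correction, 236 per arm (472 in total) would be needed. Planned accrual is 200/526 = 38% of the stated requirement.

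**2. Power at 100 per arm, 12% versus 4.85%.**

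- Normal approximation: z = [d·√100 − 1.960 × 0.3928] / 0.3895 = (0.7150 − 0.7699)/0.3895 = −0.141, so power is 44.4%.
- With the continuity correction behind the 263: the effective size is (2·100·d − 2)² / (4·100·d²) = 74.0 per arm, z = −0.398, power 34.5%.
- Exact: summing the binomial probabilities of every pair of event counts for which the test gives P < 0.05.

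| Method at 100 per arm | Power |
|---|---|
| Student's t test (the planned test), exact enumeration | 45.8% |
| Normal approximation, uncorrected | 44.4% |
| Fisher's exact test, exact enumeration | 35.5% |
| Normal approximation, continuity corrected | 34.5% |

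**3. What 100 per arm could detect with 80% power, p1 = 12%.**

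| Method | Second rate needed | Relative reduction |
|---|---|---|
| t test, exact enumeration | about 2.3% | 81% |
| Formula, uncorrected | 1.96% | 84% |
| Fisher, exact enumeration | about 1.7% | 86% |
| Formula, continuity corrected | 1.22% | 90% |

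The plan assumes a 60% reduction.

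**4. Precision.** If exactly 12% and 4.85% were observed, SE = √[(0.1056 + 0.0461)/100] = 0.0390. The 95% interval is 7.15 ± 1.96 × 3.90 points, or −0.5 to +14.8 points, which includes zero.

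**5. Does the interim look help?** It halts the trial only at P < 0.001 after 100 subjects. With 50 per arm and the planned rates, the chance of crossing is 0.9% (t test) or 0.4% (Fisher), so it adds almost nothing.

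**The case against.** The strongest reply is that the plan never says 200 subjects give 80% power. The 80% is an input to a calculation whose answer, 263 per arm, is printed beside it, and the text says openly that enrolment follows transplant volume. On this reading the shortfall is visible and only its size is left unstated. Much of that stands: the arithmetic is correct, and the defect is a mismatch left undisclosed. But the feasibility sentence explains why 200 was chosen. It does not say that 200 is well under half the requirement, nor what power is left.

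A second reply is that the control rate may exceed 12%. With the same relative reduction, t-test power at 100 per arm would be 56% at a 15% rate, 70% at 20% and 81% at 25%. Those rates are assumptions that the documents do not support; 12% is the only rate the plan uses, and it is already an upward revision. So the 35–46% is conditional on 12%, but the plan offers no basis for a higher figure.

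A third reply is that the 1:1 ratio appears only in the calculation. That is so, but no other ratio is given, and unequal allocation of this size or any losses would generally reduce precision.

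Last, a wording-only remedy might suggest a minor point. The remedy is cheap, but power below one half for the plan's own effect determines what a null result can mean.

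**Conclusion.** The concern holds. For the effect the plan itself assumes, the trial as planned has about 35–46% power, depending on the test, instead of the 80% in its only calculation; with the planned t test the figure is 45.8%. This rests on the plan's rates of 12% and 4.85%, two-sided alpha 0.05, 100 per arm and no losses. The documents give no dropout rate; losses would lower power further. The number 200 appears consistently in two sections, so it is the intended size and not a slip.

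**What to change.** Replace the power statement with one for the planned size, using one method for both power and detectable effect. For example:

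*With 100 subjects per arm (1:1, no losses), a 12% placebo rate and two-sided alpha 0.05, power to detect a reduction to 4.85% is about 46% with the t test (35.5% with Fisher's exact test), by exact enumeration. Power of 80% is reached only if the chlorhexidine rate is about 2.3% (1.7% with Fisher's exact test). The 263 per arm needed for 80% power at 4.85% was not feasible at this site.*

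State the randomisation ratio where randomisation is described. It would also help to commit to reporting the risk difference or rate ratio with a 95% confidence interval and to say that P > 0.05 will not be read as absence of effect; this is good practice beyond the correction itself.

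The cost is wording only: no extra patients and no change to conduct. The price is a less favourable stated power.

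### The planning proportions (12% vs 4.85%) cannot be derived from the data shown, and the only stated power, 80%, belongs to 263 per arm; about 100 per arm gives roughly 33–46% on the plan's own figures

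*Combined protocol and SAP*

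**What the plan says.** Statistical Plan and Considerations expects a "higher incidence of CLABSI given the previous Infection Control snapshot", applies the multiplier by "recalculating with an ~50% higher outpatient rate", and prints the Stata command "sampsi 0.12 0.0485, power(0.8") with its output: two-sided alpha 0.05, power 0.80, equal arms, 263 per arm. It does not give the rate that was raised by half, or a source for 0.12 or 0.0485.

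The only inpatient and outpatient CLABSI data in the document are in the table under Setting and Participants, covering September 2007 to August 2008. The text introducing it says that "the outpatient data will be used as our initial data control group". The table lists numbers of infections by nursing unit: 36 hospital-acquired and 76 present on admission in total. It gives no patients, discharges or catheter-days, and does not say which unit houses the transplant patients.

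On size, the same statistical section states "The plan is to accrue up to 200 subjects" and explains that "we based the numbers of patients on the number of HSC transplants performed annually". No power is given for that number.

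The background section reports one numerical effect size, a 40% fall in CLABSI rates after a multi-component prevention programme.

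**The concern.** Two things are missing. First, a reader cannot trace the planning proportions. The multiplier, the base rate and the treatment-arm rate are each unsourced, and the cited snapshot, if it is the table, cannot supply them.

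Second, the one power statement in the plan describes 526 subjects (2 × 263), while at most 200 will be accrued. Nothing says what 200 can detect.

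The stake is interpretation. The plan foresees early looks to judge whether continuing is appropriate, and a final comparison that may well be non-significant. If power is well under one half on the plan's own assumptions, a non-significant result says little about whether the washcloths work, and the protocol should say so in advance.

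**Working it through.** **Inputs.** p1 = 0.12, p2 = 0.0485, two-sided alpha 0.05, power 0.80 and ratio 1:1 (sample-size printout); up to 200 subjects, taken as 100 per arm (same section; equal split as in the printout); 36 and 76 infections (CLABSI table); 40% reduction (background).

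**1. The plan's own figure.** Mean proportion 0.08425; difference 0.0715.

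- √(2 × 0.08425 × 0.91575) = 0.3928
- √(0.12 × 0.88 + 0.0485 × 0.9515) = 0.3895
- n = (1.96 × 0.3928 + 0.8416 × 0.3895)² / 0.0715² = 235.7
- With continuity correction: n/4 × (1 + √(1 + 4/(n × 0.0715)))² = 262.95, i.e. 263 per arm

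The printed 263 follows from its inputs.

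**2. Can the inputs be derived?**

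- Total counts: 76/36 = 2.11, or +111%.
- By unit (outpatient vs inpatient): T6NW 18 vs 32, T6NE 30 vs 1, T6SW 28 vs 3. None is near +50%.
- Base rate implied for the control arm: 0.12/1.5 = 0.08. This figure appears nowhere.
- Relative reduction: 1 − 0.0485/0.12 = 59.6%. No source is given.
- The text does not say whether both proportions were scaled or only the control rate. If only the control rate was, 4.85% against the unscaled 8% is 1 − 0.0485/0.08 = 39%. The document does not settle this.

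**3. Power at the planned size.** Normal approximation, 100 per arm, 12% vs 4.85%:

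- Critical difference: 1.96 × 0.3928/√100 = 0.0770
- Standard error under the alternative: 0.3895/√100 = 0.03895
- Uncorrected: Φ((0.0715 − 0.0770)/0.03895) = Φ(−0.141) = 0.44
- Corrected (difference less 1/100): Φ((0.0615 − 0.0770)/0.03895) = Φ(−0.398) = 0.35

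The figures below come instead from full binomial enumeration: the probabilities of all pairs of event counts in 100 and 100 for which the pooled two-sided z statistic reaches 1.96, added up.

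| Control | Treatment | Relative reduction | Power, corrected | Power, uncorrected |
|---|---|---|---|---|
| 12% | 4.85% | 60% (plan) | 33% | 46% |
| 12% | 7.2% | 40% | 14% | 21% |
| 9% | 3.64% | 60% | 23% | 34% |
| 38% | 15.4% | 60% | 94% | 96% |

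The 9% and 38% rows are illustrations only: 18/200 and 76/200, which assume that the relevant infections all occurred in transplant patients in a year with 200 transplants. The document states neither. For 12% vs 7.2%, the formula in step 1 gives 632 per arm.

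**The case against.** The strongest reply is that these proportions do not set the trial's size. The plan says openly that numbers follow transplant volume, and by printing 263 per arm beside a ceiling of 200 it lets any reader see the shortfall. That stands. A reader might infer that the protocol claims 80% power for 200 subjects; it does not. What remains is that it never says what 200 does provide.

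Two other stronger readings should be resisted.

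- *A reader might infer that the table contradicts the 50% multiplier.* It cannot. The plan speaks of a rate and the table gives counts. A count ratio of 2.11 is compatible with a rate ratio of 1.5 if outpatient exposure was about 1.4 times inpatient exposure (2.11/1.5). The table total also agrees in direction with the plan's premise. T6NW alone runs the other way, but the document does not identify it as the transplant unit, and its counts lack denominators too. That the snapshot is this table is itself an inference, though no other candidate is shown.
- *A reader might infer that 263 per arm is wrong or baseless.* It is correct arithmetic on the printed inputs. Only the inputs lack a source.

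It is also fair to say that power is not low under every control rate: a rate as high as 38% would be well served by 100 per arm at a 60% reduction. That supports showing a range. Finally, the 40% figure comes from a bundle in hospital units, so it is a reference point and not an estimate for washcloths at home.

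**Conclusion.** The point holds as a gap in derivation together with a power statement that does not describe the planned trial. The multiplier, both proportions and the 60% reduction cannot be traced to anything in the document. At about 100 per arm the plan's own proportions give 33% power (continuity-corrected) to 46% (uncorrected), not 80%. Put the other way, if the assumed effect were real, the trial would miss it 54–67% of the time. With a 40% reduction from 12%, power is 14–21%.

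These figures assume equal arms, all 200 subjects evaluable, two-sided alpha of 0.05 at the final analysis and no allowance for the interim look. The range in each pair reflects only the choice of continuity correction. The documents do not allow a better control rate to be named, so no replacement sample size is offered.

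**What to change.** Rewrite the sample-size paragraph under Statistical Plan and Considerations:

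1. Remove the 50% multiplier, or give its source with numerator and denominator.
2. Define p1 as the risk of a first outpatient CLABSI per transplant patient discharged with a central line. If no data support p1 and p2, label both as assumptions.
3. Replace the printout with power at 100 per arm for control rates of, for example, 5%, 9%, 12%, 17% and a high case, each with relative reductions of 40% and 60%. State the test and whether it is continuity-corrected.
4. State that enrolment is set by transplant volume and that 80% power is not provided under the plan's own assumptions.

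Enrolment and procedures do not change. The cost is one rewritten paragraph and, if the site holds denominators (the document does not say), a query of existing infection-control data. The downside is a less favourable stated power.
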